Finally, to determine the minimum effective dose, a phase IIa, double-blind, randomized, placebo-controlled, dose escalating (0.5-1.0-1.5 µg/kg/min) efficacy study (HORIZON-HF) was conducted assessing the hemodynamic effects of istaroxime in 120 patients hospitalized with worsening HF and reduced left ventricle systolic function [14]. The primary end point of the study was the change from baseline in PCWP after 6 hours of infusion. Dose-dependent improvements in PWCP were observed with a statistically significant effects of all the 3 istaroxime doses versus placebo (- 3.21 mmHg with the $0.5 \mu g/kg/min dose$, $-3.33 mmHg with the <math>1.0 \mu g/kg/min dose$, and -4.73 mmHg with the1.5 μg/kg/min dose). HR tended to decrease during the 6-hour infusion but no significant differences were observed at infusion end between treatment groups. Systolic blood pressure (SBP) slightly increased dose-dependently in all istaroxime-treated groups but not in the placebo group, reaching a statistically significant difference from the dose of 1.0 µg/kg/min. A trend towards an increase in cardiac output was also observed in the treated groups. A significant increase in cardiac index (CI) was observed only in patients with a CI<2.5 at baseline. Statistically significant difference between istaroxime and placebo were found for LV end systolic volume at 1.0 µg/kg/min and for LV end diastolic volume at 1.5 μg/kg/min. Doppler echocardiography and tissue Doppler imaging showed changes in the E/Ea parameter that resulted statistically significant at 0.5 $\mu g/kg/min$ (-3.8, p= 0.03) and close to significance at 1.0 $\mu g/kg/min$ (-1.12, p= 0.059). In conclusion, echocardiographic data showed istaroxime to improve diastolic and systolic volumes, as well as Doppler and tissue Doppler parameters of diastolic function. As far as safety concerns, this study showed an increase in gastrointestinal TEAEs in the highest dose group (1.5 µg/kg/min) in which 10% and 17% of patients experienced nausea and vomiting, respectively. No patients experienced serious or clinically relevant episodes of arrhythmia during the infusion and post-infusion period. A mild increase in the frequency of isolated ventricular extrasystoles was found in the 1.5 µg/kg/min group in 8 out of 30 patients. It is difficult to ascertain whether this increase was related to drug infusion or to spontaneous variability of patients, because of insufficient baseline recordings. One patient out of 30 in the istaroxime 1.5 µg/kg/min group experienced tachycardia with angina and ST-change during infusion. The QTc interval measured at 6 hours after infusion was shortened by -25, -38 and -49 ms at the three Istaroxime doses, respectively

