# 4.0 STUDY DESIGN

This is a phase II, multicenter, randomized, double-blind, placebo-controlled, parallel group study.

96 Chinese patients and 24 Italian patients will be randomly assigned to one of two doses of istaroxime or placebo in a 2:1 ratio within two sequential cohorts of 60 patients each.

1.0/30/10/2018 Page 9 of 28

This 31-day study includes a screening period (Day -1), a treatment period (Day 1), a post-treatment period (Days 2-4), and a follow-up period (which includes one patient visit on Day 30).

When a patient is considered fully eligible (i.e. s/he fulfills all the inclusion criteria and does not meet any exclusion criteria as stipulated), the patient will be randomized.

Treatment details are presented below:

**Cohort I**: 0.5 µg/kg/min istaroxime or placebo (40 patients randomized to istaroxime 0.5 µg/kg/min group and 20 patients randomized to placebo group).

Istaroxime 0.5  $\mu$ g/kg/min (30  $\mu$ g/kg/h) continuous i.v. infusion for 24 hours not exceeding 72 mg per 24 hours for patients with body weight > 100 kg.

**Cohort II**: 1.0 μg/kg/min istaroxime or placebo (40 patients randomized to istaroxime 1.0 μg/kg/min group and 20 patients randomized to placebo group).

Istaroxime 1.0  $\mu$ g/kg/min (60  $\mu$ g/kg/h) continuous i.v. infusion for 24 hours not exceeding 144 mg per 24 hours for patients with body weight > 100 kg.

A total of 96 Chinese and 24 Italian patients hospitalized with ADHF not requiring inotropic therapy at inclusion into the study (according to the opinion of the Investigator) and not presenting signs and/or symptoms of severe low output state or peripheral hypo perfusion will be randomized.

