### 7.2 COVARIATES AND SUBGROUPS

Linear Mixed Models for Repeated Measures (MMRM) will include treatment, centre, timepoint, gender, baseline cTnT (normal <URL, abnormal ≥URL), atrial fibrillation (Yes/No) and treatment\*timepoint interaction as fixed effects and baseline and baseline\*timepoint interaction as covariates.

Analysis of Covariance (ANCOVA) models will include treatment, centre, gender, baseline cTnT (normal <URL, abnormal ≥URL) and atrial fibrillation (Yes/No) as fixed effects and baseline as covariate.

ANOVA models for echocardiographic parameters will include treatment only. For analysis of Cohort 1, treatment is defined as (0.5 µg/kg/min dose, placebo). For analysis of Cohort 2, treatment is defined as (1.0 µg/kg/min dose, placebo).

All baseline values considered in the statistical analyses have been defined in the paragraph 6.6.

1.0/30/10/2018 Page 16 of 28

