# 7.4 GENERAL METHODOLOGY

Descriptive statistics will be provided for all variables in the summary tables by treatment group according to the type of variable summarized.

Quantitative variables will be summarised by using n, mean, standard deviation (SD), 95% confidence interval (CI) of the mean, median and range (minimum and maximum). Categorical variables will be summarised by using frequency distributions and percentages.

Hypothesis testing will be carried out at the alpha = 0.05 level (two-sided) when comparing treatments. For all inferential analyses, p-value will be rounded to three decimal places. Statistical significance will be declared if the rounded p-value will be less than or equal to 0.05.

Statistical analyses will be carried-out pooling together the patients treated with placebo in the two groups with the exception of the echocardiographic parameters that will be analysed separately for each cohort.

All data collected in the CRF will be presented in the listings.

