#### 7.7 ANALYSIS OF EFFICACY

# 7.7.1 Primary efficacy endpoint

Analysis will be performed separately for each cohort on ITT and PP populations.

E/Ea ratio will be summarized at each timepoint by treatment group by means of descriptive statistics.

Comparisons between treatment groups will be done using an ANOVA with change from baseline in E/Ea at 24 hours as dependent variable, and treatment as covariate.

The number of patients and the number of patients considered in the model will be provided by treatment. P-values of the fixed effects and covariates will also be presented.

The adjusted means for treatments and 95% CIs will be presented. The difference between the adjusted means for Istaroxime groups versus Placebo will be calculated with the 95% CIs and p-values.

The primary comparison will be Istaroxime 0.5  $\mu$ g/kg/min versus Placebo at 24 hours based on Cohort 1 subjects only. Highest dose of Istaroxime (1.0  $\mu$ g/kg/min) versus Placebo will be tested as a secondary comparison based on Cohort 2 subjects only.

The same analysis will be repeated for change from baseline in E/Ea at 6 hours. All treatment comparisons at 6 hours will be secondary analyses.

E/Ea ratio will also be summarized separated by cohort at each timepoint by treatment group by means of descriptive statistics.

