# 9.0 PROGRAMMING SPECIFICATIONS

The following SAS® code will be used to calculate the age of patient:

age = floor((intck('month', date of birth, date of screening)-(day(date of screening)<day(date of birth)))/12)

The following SAS® code will be used to estimate the MMRM:

```
proc mixed data = dataset;
class tmt timepoint centre gender cTnT atr_fib patient;
model change = tmt timepoint tmt*timepoint centre cTnT atr_fib gender baseline
baseline*timepoint / ddfm=kr;
repeated timepoint / subject=patient type=un;
lsmeans tmt tmt*timepoint / cl;
run;
```

where change represents the change from baseline to post-dose values of the variable, tmt the treatment group, timepoint the timepoint, centre the centre, gender the gender (male/female), cTnT the baseline cTnT (normal <URL, abnormal  $\geq$ URL), atr\_fib the atrial fibrillation (Yes/No), baseline the baseline value of the variable and patient the Patient Number.

The variable tmt will be ordered in SAS® in the following order:

- Istaroxime 0.5 μg/kg/min
- Istaroxime 1.0 µg/kg/min
- Placebo

The following SAS® code will be used to estimate the ANCOVA model:

```
proc mixed data = dataset;
class tmt centre gender cTnT atr_fib;
model variable = tmt centre gender cTnT atr_fib predose;
```

1.0/ 30/10/2018 Page 24 of 28

```
lsmeans tmt / cl; run;
```

where variable represents the efficacy variable (AUC on changes in dyspnoea by VAS score or changes in BNP), tmt the treatment group, centre the centre, gender the gender (male/female), cTnT the baseline cTnT (normal <URL, abnormal ≥URL), atr\_fib the atrial fibrillation (Yes/No), predose the pre-dose of efficacy variable.

The variable tmt will be ordered in SAS® in the following order:

- Istaroxime 0.5 μg/kg/min
- Istaroxime 1.0 μg/kg/min
- Placebo

The following SAS code will be used for the Wilcoxon rank sum test for  $T_{max}$ :

```
proc npar1way wilcoxon hl alpha=0.1 data = dataset; class tmt; var Tmax; run;
```

where tmt represents the treatment groups and Tmax the Tmax parameter value for each patient.

The following SAS code will be used for the ANOVA:

```
proc glm data = dataset;
class tmt;
model variable = tmt;
lsmeans tmt / cl;
run;
```

The following SAS code will be used for the MANOVA:

```
proc glm data = dataset;
class tmt;
model variable = tmt;
contrast 'active vs placebo' group 1 -1;
manova h=tmt;
lsmeans tmt / cl;
run;
```

The global test p-value from Pallai's Trace will be reported.

1.0/30/10/2018 Page 25 of 28

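### The primary E/Ea test assumes equal variances with 40 versus 20 patients; prespecifying arm-specific variances would protect its p-value and CI at almost no cost

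*SAP*

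**What the plan says.** SAP 7.7.1 compares the arms "using an ANOVA with change from baseline in E/Ea at 24 hours as dependent variable, and treatment as covariate". SAP 7.2 confirms that "ANOVA models for echocardiographic parameters will include treatment only". In SAP 9.0, under the line "The following SAS code will be used for the ANOVA", the model is PROC GLM with "model variable = tmt". With two arms this is the pooled-variance t-test.

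The primary contrast is 0.5 µg/kg/min "versus Placebo at 24 hours based on Cohort 1 subjects only". SAP 4.0 gives that cohort 40 patients on istaroxime and "20 patients randomized to placebo group". SAP 7.4 adds: "Hypothesis testing will be carried out at the alpha = 0.05 level (two-sided) when comparing treatments". SAP 7.7.2 applies a similar ANOVA to the secondary echocardiographic endpoints in both cohorts.

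No unequal-variance or rank-based analysis of E/Ea is planned. Neither document gives an SD for the change in E/Ea, and Protocol 14.2 and SAP 4.1 both say that no formal sample size calculation was made. The only quantitative background is in Protocol 1.2. It reports 6-hour E/Ea results from the earlier phase IIa trial of -3.8 (p=0.03) at 0.5 µg/kg/min and -1.12 (p=0.059) at 1.0 µg/kg/min.

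**The concern.** With equal arms the pooled t-test tolerates unequal variances well. With 2:1 arms it does not: 39 of the 58 residual degrees of freedom come from the active arm, so the pooled variance mostly reflects that arm, while the smaller placebo arm contributes more per unit of variance to the true standard error. If the active arm is the more variable, the standard error is too large, the CI too wide, and power is lost. If placebo is the more variable, the standard error is too small and false positives exceed 5%.

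The two earlier E/Ea results give a reason to ask the question. An effect of 3.8 with p=0.03 and an effect of 1.12 with p=0.059 are hard to reconcile with one common standard error. At stake is the calibration of the trial's only primary p-value and its interval.

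**Working it through.** **Plan's own figure.** There is none to reproduce: no SD, difference or power is stated.

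**1. Calibration at 40 versus 20.** Simulated normal data, two-sided 5%, at least 200,000 trials per scenario; repeated runs agree to about 0.2 percentage points.

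| Active SD / placebo SD | Pooled ANOVA, type I error |
|---|---|
| 0.8 | 6.7% |
| 1.0 | 5% |
| 1.25 | 3.5% |
| 1.5 | 2.7% |
| 2.0 | 1.8% |
| 2.76 | 1.2% |

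Welch stays at about 5% in every row. At 29 versus 29 with ratio 2.76 the pooled test gives 5.2%, so the problem comes from the unequal allocation. If the 20% drop-out limit of Protocol 15 were fully used (32 versus 16), the pooled figure at ratio 2.76 is 1.3%.

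**2. What the earlier figures imply if they are placebo differences.** Inputs: the two effects and p-values in Protocol 1.2, and 29 patients in both the 0.5 and placebo groups (Protocol 14.2). Assumptions: t-type tests, and 29 in the 1.0 arm, whose size is not given.

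SE = |difference| / t, with 56 degrees of freedom:
- 0.5: t = 2.227, SE = 3.8 / 2.227 = 1.706
- 1.0: t = 1.927, SE = 1.12 / 1.927 = 0.581

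With SE 1.706, a difference of 1.12 would have p = 0.51, not 0.059. The two results therefore cannot share one standard error.

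With n = 29 per arm, SE² = (SD²active + SD²placebo) / 29:
- 0.5 and placebo: variances sum to 29 × 1.706² = 84.45
- 1.0 and placebo: variances sum to 29 × 0.581² = 9.79

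Placebo is common to both, so:
- placebo SD ≤ √9.79 = 3.13
- 0.5-arm SD ≥ √(84.45 − 9.79) = 8.64
- ratio ≥ 8.64 / 3.13 = 2.76, with the larger SD in the larger arm

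**3. Consequence in Cohort 1 at those SDs.**
- True SE = √(8.64²/40 + 3.13²/20) = 1.53
- Pooled SE = √[((39 × 8.64² + 19 × 3.13²) / 58) × (1/40 + 1/20)] = 2.00
- Mean 95% CI half-width: 3.98 pooled, 3.06 Welch (3.98 / 3.06 = 1.30)
- Power for a difference of 3.8: 45% pooled, 68% Welch

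**4. Other readings of the same figures.**
- Within-arm changes with p-values against placebo: the minimum ratio depends on the unstated placebo change. It is 1.7, 1.3 and 1.0 for placebo changes of +1, +2 and +3.
- Paired within-arm tests: SD = |change| × √29 / t, with 28 degrees of freedom. This gives 3.8 × √29 / 2.286 = 8.95 and 1.12 × √29 / 1.968 = 3.06. Both belong to active arms, so nothing follows about placebo.

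**The case against.** The strongest reply is that the heterogeneity is inferred, not documented. Protocol 1.2 does not say whether -3.8 and -1.12 are placebo differences or within-arm changes, names no test, and gives no size for the 1.0 arm. The data are from 6 hours in another trial, whereas the endpoint here is at 24 hours. The favoured reading is also odd in itself: it needs a very large SD at the lower dose and a small one at twice that dose. A misprint, an outlier, covariate adjustment or fewer evaluable echocardiograms could produce the same pattern. All of this stands.

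In its favour, Protocol 14.2 does describe the 0.5 result as significant relative to placebo, which supports the placebo-difference reading for that arm without settling it.

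A reader might infer from the unequal arms that the primary test has an inflated false-positive rate. The documents do not support that. Inflation needs the larger SD in placebo, and on the one reading that bears on placebo the larger SD is in the active arm. A reader might also extend the finding to Cohort 2 or to the other echocardiographic parameters. The 1.0 figure bounds only a sum of two variances, and equal SDs of 2.21 fit it exactly (2 × 2.21² ≈ 9.8). For the other parameters Protocol 1.2 gives nothing from which SDs could be derived.

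Two mitigating points have limited force. SAP 7.4 reports SDs by treatment group, so unequal variances would be visible, but the p-value would not change. SAP 1.1 places the rationale for the ANOVA in a memo that was not available for this review. SAP 7.7.2 does weigh sensitivity to unequal covariances in smaller samples when choosing the MANOVA statistic, so the issue was recognised there but not carried to the primary test.

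**Conclusion.** The concern holds as a robustness gap. The primary analysis is a pooled-variance, treatment-only comparison of 40 versus 20 patients with no unequal-variance alternative, and its p-value and CI may be miscalibrated if the arm SDs differ. A ratio of 0.8 or 1.25 is enough to move the error rate to about 6.7% or 3.5%.

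It would be too strong to say that the result is miscalibrated, or that the arms are known to differ threefold. The ratio of at least 2.76 rests on placebo differences, t-type tests, about 29 patients per arm, and carry-over from 6 to 24 hours. If those assumptions hold, the fault is conservatism: type I error near 1%, a CI about 30% wider than Welch's, and 45% rather than 68% power at a difference of 3.8. This is a cheap improvement to the plan, not an error in it as written.

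**What to change.** In SAP 7.2, 7.7.1 and 9.0, prespecify arm-specific variances for the primary E/Ea comparison, for example:

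`proc mixed; class tmt; model change = tmt / ddfm=satterthwaite; repeated / group=tmt; lsmeans tmt / diff cl; run;`

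For two arms this is the Welch comparison. Use the same form for the other echocardiographic ANOVAs in SAP 7.7.2, for consistency rather than because heterogeneity has been shown there. Keep the pooled ANOVA as a named sensitivity analysis. Fix the choice before unblinding, because choosing between the two after seeing the SDs would be data-driven.

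The cost is a few words in the SAP and a short change of code. If the variances are in fact equal, power falls by under 1 percentage point (about 81.0% against 81.7% at a difference of 0.8 SD).

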# 7.7.2 Secondary efficacy endpoints

For echocardiographic parameters, analysis will be performed separately for each cohort on ITT population.

For all other endpoints, analysis will be performed using the combined cohorts on ITT population.

# Echocardiographic parameters

The following secondary endpoints:

o LVEF

1.0/30/10/2018 Page 19 of 28

- o LV end systolic and end diastolic volumes
- o SVI, and CI
- o E, A, E/A ratio
- Sa (tissue doppler parameters)
- o Ea and TAPSE

will be summarized at each timepoint by treatment group by means of descriptive statistics.

Comparison between treatment groups will be done using the ANOVA similar to the one used for the primary efficacy endpoint. Only change from baseline echocardiographic data at 6 hours and 24 hours values will be analyzed.

The global test using multivariate analysis of variance (MANOVA) considering multiple echocardiographic parameters will also be performed separately at 6 and 24 hours and by cohort for echocardiographic parameters grouped into 3 types of cardiac mechanics:

- Relaxation parameters such as: E/Ea, Ea
- Contraction parameters such as: Sa, TAPSE
- Overall cardiac pumping ability parameters such as: SVI, CI

The MANOVA p-value from Pallai's Trace will be reported. ((Olson (1976) suggests that Roy's largest root is too likely produce Type I errors and should be avoided, that Wilk's lambda and Hotelling's trace are sensitive to violations of equal covariances in smaller samples, and he recommends Pillai's trace for general use.)

## Dyspnoea using VAS score

Analysis will be performed only for patients with VAS score at screening different from 100 or missing.

Dyspnoea using VAS score and changes from baseline will be summarized at each timepoint by treatment group by means of descriptive statistics.

Changes in dyspnoea using VAS score will be analyzed using a MMRM with change from baseline in dyspnoea using VAS score at 3, 6, 12, 24, 48 hours as dependent variable, treatment, centre, timepoint, gender, baseline cTnT (normal <URL, abnormal ≥URL), atrial fibrillation (Yes/No) and treatment\*timepoint interaction and baseline and baseline\*timepoint interaction as covariates. An unstructured covariance matrix will be considered and the Kenward-Roger adjustment will be used for the degrees of freedom. Only pre-dose, 3, 6, 12, 24, 48 hours values after infusion start will be considered in the MMRM.

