6. CLINICAL ENDPOINTS

6.1 Efficacy Endpoints

1. Primary efficacy end-points:

• Change from baseline to 24 hours after infusion start (treatment period Day 1) in the E/Ea ratio assessed by tissue Doppler.

2. Secondary efficacy end-points:

- Change from baseline to 24 hours in the treatment period Day1 (addressing the differences between the changes at 6 and 24 hours from baseline) of the following Echo-Doppler parameters:
 - LV Ejection Fraction (EF)
 - LV end systolic and end diastolic volumes
 - Stroke volume index (SVI)

- E, A and E/A ratio
- Change from baseline to 24 hours in the E/Ea ratio assessed by tissue Doppler (difference between the changes at 6 and 24 hours from baseline)
- Others Tissue Doppler parameters such as Sa, Da and Aa
- Changes in dyspnea assessed at 3, 6, 12, 24, 48 hours after infusion start by Visual Analog Scale (VAS) (including only patients presenting dyspnea at baseline);
- Area under the curve (AUC) on changes in dyspnea assessed at 3, 6, 12, 24, 48 hours after infusion start by VAS (including only patients presenting dyspnea at baseline);
- Changes in BNP from baseline at 24 hours;
- Proportion of patients with hospital readmissions or emergency visits for cardiovascular reasons by Day 30;
- Proportion of patients with episodes of worsening HF defined by the need to increase the dose or reinitiate i.v. therapy with diuretics and/ or other inotropic agents during the hospitalization;
- Length of hospitalization.

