8. EFFICACY ASSESSMENTS

Change from baseline to 24 hours after infusion start in the E/Ea ratio assessed by tissue Doppler will be assessed as primary end-point. Other echocardiographic parameters (LVEF, LV end diastolic and end systolic volumes, SVI, E/A ratio, other Tissue Doppler parameters such as Sa, Da and Aa) will be assessed as secondary end-points. These parameters will be assessed also at 48 hours as further exploratory analyses.

Dyspnoea will be assessed at baseline using a 100 mm VAS scale. Further assessments will be repeated at 3, 6, 12, 24 and 48 hours after the start of drug infusion only in patients presenting dyspnoea at baseline.

NT-proBNP will be measured by the local laboratory only for evaluation and screening inclusion. While at baseline, at 24 hours after infusion start (day 2), on Day 3, at day 4 or at discharge) and at day 30, NT-proBNP will be measured by the central laboratory

Episodes of worsening HF, defined by the need to increase the dose or reinitiate i.v. therapy with diuretics and/ or other inotropic agents during the hospitalization, will be recorded.

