# 3.2.2 Secondary Endpoints

The secondary efficacy endpoints are the following:

- Change from baseline to 24 hours in the treatment period Day 1 (addressing the differences between the changes at 6 and 24 hours from baseline) of the following Echo-Doppler parameters:
  - o Left Ventricular Ejection Fraction (LVEF)
  - o LV end systolic and end diastolic volumes
  - o Stroke volume index (SVI), and CI
  - o E, A and E/A ratio
  - o Ea and TAPSE
- Change from baseline to 24 hours in the E/Ea ratio assessed by tissue Doppler (difference between the changes at 6 and 24 hours from baseline)
- Others tissue doppler parameters such as Sa;
- Changes in dyspnoea assessed at 3, 6, 12, 24, 48 hours after infusion start by Visual Analog Scale (VAS) (including only patients presenting dyspnoea at baseline);

1.0/30/10/2018 Page 8 of 28

- Area under the curve (AUC) on changes in dyspnoea assessed at 3, 6, 12, 24, 48 hours after infusion start by VAS (including only patients presenting dyspnoea at baseline);
- Changes in Brain Natriuretic Peptide (BNP) from baseline at 24 hours;
- Proportion of patients with hospital readmissions or emergency visits for cardiovascular reasons by Day 30;
- Proportion of patients with episodes of worsening heart failure defined by the need to increase the dose or reinitiate i.v. therapy with diuretics and/ or other inotropic agents during the hospitalization;
- Length of hospitalization.

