# 6.3 EFFICACY VARIABLES

# AUC0-48h on changes in dyspnoea

AUC0-48h on changes in dyspnoea will be calculated using the following formula:

$$AUC_{0-48h} = \sum_{i=3h}^{48h} \frac{(t_i - t_{i-1})(\Delta VAS_i + \Delta VAS_{i-1})}{2}$$

with i = 3, 6, 12, 24, 48 hours.

1.0/30/10/2018 Page 13 of 28

In the above formula,  $t_i$  represents the scheduled timepoints in hours for VAS score measurements (see table below) and  $\Delta VAS_i$  represents the change from pre-dose of the value of the VAS score at the timepoint i. The change from pre-dose at the timepoint i = 0 will be zero.

Time of evaluation (hours)					
T pre- dose	T3h	T6h	T12h	T24h	T48h
$t_0$	$t_1$	t 2	t 3	t 4	t 5
Time point for calculation					

The scheduled timepoint will be used for the calculation of AUC0-48h.

In the calculation of  $AUC_{0-48h}$ , missing values will be replaced as follows:

- single, isolated missing values (different from pre-dose and last value) will be replaced by linear interpolation using the adjacent values;
- if the last value is missing, it will be replaced by the previous value;
- in case of pre-dose value is missing and/or two or more consecutive values are missing and/or three or more values are missing, no replacement will be performed and the entire curve will be considered as missing.

The AUC0-48h will be calculated after the replacement of missing values.

AUC0-48h will be calculated only for patients with VAS score at screening different from 100 or missing.

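### The two dyspnoea analyses select patients on the screening VAS, although the endpoints are restricted to dyspnoea at baseline and the SAP sets the VAS baseline at pre-dose Day 1

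*SAP*

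**What the plan says.** **Selection rule.** SAP 7.7.2, under the dyspnoea VAS heading: "Analysis will be performed only for patients with VAS score at screening different from 100 or missing". The AUC heading in 7.7.2 repeats the sentence. The derivation in SAP 6.3 says that the AUC "will be calculated only for patients with VAS score at screening different from 100 or missing".

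**Endpoint population.** Protocol 6.1 defines both dyspnoea endpoints as "including only patients presenting dyspnea at baseline", and SAP 3.2.2 agrees: "including only patients presenting dyspnoea at baseline".

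**Baseline.** The table in SAP 6.5 gives pre-dose Day 1 as the baseline for the dyspnoea VAS. Screening is the baseline only for laboratory parameters and renal function.

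**Other parts of the two analyses.** In the AUC formula each delta term "represents the change from pre-dose of the value of the VAS score at the timepoint i". For the repeated-measures model: "Only pre-dose, 3, 6, 12, 24, 48 hours values after infusion start will be considered in the MMRM". The ANCOVA code in SAP 9.0 uses the pre-dose value as covariate.

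**Data collection.** Protocol section 8 takes the 100 mm VAS at baseline and repeats it after the infusion starts "only in patients presenting dyspnoea at baseline". Protocol section 7 lists dyspnoea at screening and again at pre-dose.

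**Declared changes.** SAP 1.1 lists changes from the protocol for echocardiographic parameters only. It mentions no change to the dyspnoea population.

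**The concern.** The filter is evidently meant to implement the restriction to patients with dyspnoea at baseline, but it reads the wrong visit. Protocol section 7 allows screening up to 24 hours before dosing, and section 5.7 lets i.v. diuretics be given in that period to stabilise the patient. Dyspnoea can therefore differ between screening and pre-dose. Where it does, the written rule selects a different patient from the one the endpoint describes.

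Two secondary endpoints are affected: the VAS repeated-measures model and the AUC0-48h. At stake is whether they are analysed in the population that both documents define, and whether they lose precision or are diluted by patients who cannot improve. The primary E/Ea endpoint is not affected.

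**Working it through.** The documents give no sample size, effect size or SD for dyspnoea, so there is no stated figure to reproduce. The check sets the rule beside the definition and then shows what a mismatch could cost.

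**1. Rule against definition.** Assumption: 100 means no dyspnoea. The filter implies this, but neither document states the scale direction.

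| Screening VAS | Pre-dose VAS | SAP filter | Endpoint definition with SAP 6.5 |
|---|---|---|---|
| below 100 | below 100 | in | in |
| below 100 | 100 | **in** | **out** |
| 100 | below 100 | **out** | **in** |
| 100 | 100 | out | out |
| missing | below 100 | unclear | in |
| missing | 100 | unclear | out |

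The rule fails in rows 2 and 3. The last two rows are open because the sentence can be read two ways: the score must be neither 100 nor missing (patient removed), or it may be anything but 100, or absent (patient kept).

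**2. What a row 2 patient can contribute.** The SAP 6.3 formula is AUC = Σ (tᵢ − tᵢ₋₁)(Δᵢ + Δᵢ₋₁)/2, with t = 0, 3, 6, 12, 24, 48 h and Δ₀ = 0.
- Pre-dose 100: every Δ is 0 or negative, so the largest possible AUC is 0.
- Pre-dose 50, full relief from 3 h: 3 × (0 + 50)/2 + 45 × 50 = 75 + 2250 = 2325 mm·h.

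Such a patient can only pull a mean improvement down, and only if post-dose scores exist.

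**3. Counts, by assumption only.** If 2% to 20% of the 120 patients differed in status between the two readings, that would be 120 × 0.02 = 2.4 to 120 × 0.20 = 24 patients. Neither end has a source in the documents.

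**4. Cost in power, by assumption only.** SAP 7.4 and 7.7.2 pool the cohorts for dyspnoea, giving 40 per arm. Assume a standardised effect of d = (1.960 + 0.842) × √(2/40) = 0.626, which gives 80% power at two-sided 0.05. Power = Φ(d√(n/2) − 1.96). Let q be the affected share.

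| q | Wrongly kept, with data: n = 40, effect d(1 − q) | Same patients removed: n = 40(1 − q), effect d |
|---|---|---|
| 5% | 75.9% | 78.0% |
| 10% | 71.3% | 75.7% |
| 20% | 61.1% | 70.7% |

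The last column is also the power if the screening rule wrongly drops a share q of eligible patients; the comparison is then with 80%. Losing 10% of patients widens a confidence interval by 1/√0.9 = 1.054, about 5%.

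**5. Whether a pre-dose rule needs extra data.** It does not. SAP 6.3 already treats the whole curve as missing when the pre-dose value is missing, and the repeated-measures model needs that value both for the change and for the baseline covariate. The screening rule instead brings in a second value that neither analysis otherwise uses.

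**The case against.** The case against reading much into this is strong on consequences.

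- **Symptom-free patients may not enter the analysis.** Protocol section 8 limits post-dose VAS to patients with dyspnoea at baseline. If sites follow it, a row 2 patient has no change scores for the model, and under SAP 6.3 two or more consecutive missing values void the AUC. This largely stands. Some risk remains because the vital-sign lists also record dyspnoea, without naming the VAS.
- **Wrong dropping should be rare.** Inclusion criterion 3 requires admission with dyspnoea at rest or minimal exertion, so a screening score of exactly 100 followed by dyspnoea at pre-dose is unlikely. This stands.
- **There is no bias.** Both readings precede dosing, so the filter cannot depend on response to treatment. This stands.

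A reader might infer more than the documents support in three ways. First, that patients without a screening VAS are excluded and complete series lost: the sentence does not settle this, and how complete the screening VAS is cannot be judged without the CRF. Second, that the screening VAS precedes the stabilising diuretics: protocol 5.7 says only that these are given during the screening period, not in which order. Third, that some particular percentage of patients is misclassified: no such figure can be derived.

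None of this removes the mismatch. The SAP still names a visit that disagrees with its own baseline table and with both statements of the endpoint.

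**Conclusion.** The inconsistency is real but minor. In three places the SAP selects on the screening VAS, while the defined population, read with SAP 6.5, is set at pre-dose Day 1. Patients can be misclassified in both directions, and a missing screening score is handled ambiguously.

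The harm is an analysed population that departs from the defined one, with possible dilution or loss of precision in two secondary endpoints. It is not bias in the randomised comparison. The number affected cannot be derived and is probably small: wrong dropping is made rare by the entry criterion, and most wrongly kept patients should have no post-dose VAS. The counts and powers shown are conditional on assumed shares and an assumed effect, and the power for wrongly kept patients also requires that they have post-dose scores. The direction of each misclassification rests on 100 meaning no dyspnoea.

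**What to change.** In SAP 6.3 and under both dyspnoea headings of 7.7.2, replace the selection rule with: *patients with a non-missing pre-dose Day 1 (baseline) VAS score different from 100*. State in SAP 6.3 that 100 denotes no dyspnoea, if that is the scale direction.

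Changing only the visit name would not be enough. The missing-value ambiguity would carry over, and on one reading the sentence would admit patients with no pre-dose score, who can have no change from baseline.

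The cost is one sentence in three places and a line on the scale. No new data are needed, and no patient is lost for lack of a pre-dose score who could otherwise be analysed.
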